8.4.3. Follow-up of Adverse Events and Serious Adverse Events

The investigator is obligated to perform or arrange for the conduct of supplemental measurements and evaluations as medically indicated to elucidate the nature and causality of the AE, SAE, or PQC as fully as possible. This may include additional laboratory tests or investigations, histopathological examinations, or consultation with other health care professionals.

Adverse events, including pregnancy, will be followed by the investigator as specified in Section 10.4, Appendix 4: Adverse Events, Serious Adverse Events, Product Quality Complaints, and Other Safety Reporting: Definitions and Procedures for Recording, Evaluating, Follow-up, and Reporting.

8.4.4. Regulatory Reporting Requirements for Serious Adverse Events

The sponsor assumes responsibility for appropriate reporting of AEs to the regulatory authorities. The sponsor will also report to the investigator (and the head of the investigational institute where required) all suspected unexpected serious adverse reactions (SUSARs). The investigator (or sponsor where required) must report SUSARs to the appropriate Independent Ethics Committee/Institutional Review Board (IEC/IRB) that approved the protocol unless otherwise required and documented by the IEC/IRB. A SUSAR will be reported to regulatory authorities unblinded. Participating investigators and IEC/IRB will receive a blinded SUSAR summary, unless otherwise specified.

8.4.5. Pregnancy

All initial reports of pregnancy in partners of male participants must be reported to the sponsor by

Clinical Protocol 42847922ALZ2001 Amendment 1

the study-site personnel within 24 hours of their knowledge of the event using the appropriate pregnancy notification form. Abnormal pregnancy outcomes (eg, spontaneous abortion, fetal death, stillbirth, congenital anomalies, ectopic pregnancy) are considered SAEs and must be reported using the Serious Adverse Event Form.

Because the effect of the study drug on sperm is unknown, pregnancies in partners of male participants included in the study will be reported as noted above.

Follow-up information regarding the outcome of the pregnancy and any postnatal sequelae in the infant will be required.

8.4.6. Adverse Events of Special Interest

The following AEs are considered to be of special interest in this study:

- Somnolence (eg, sleepiness, drowsiness)
- Cataplexy (sudden, transient episode of muscle weakness accompanied by conscious awareness)
- Sleep paralysis (the experience of not being able to move, react, or speak when falling asleep/awakening)
- Complex, sleep-related behaviors/parasomnias such as confusional arousals, somnambulism (sleep walking), sleep terrors, bruxism (teeth grinding), sleep sex, sleep related eating disorder, and catathrenia (REM-associated end-inspiratory apnea/breath holding)
- Fall (defined as an event which results in a person coming to rest inadvertently on the ground or floor or other lower level, falling, loss of posture, falling down)
- Motor vehicle accident (also referred to as a road traffic accident, traffic collision, or a car accident, occurs when a motor vehicle strikes or collides another vehicle, a stationary object, a pedestrian, or an animal)

Investigators are instructed to inquire about the occurrence of such events during the collection of AEs at each visit. When reported, the investigator will be required to complete additional eCRF pages for AESI. Note: If the event meets the seriousness criteria (see Section 10.4.1, Appendix 4: Adverse Events: Definitions and Classifications), the Serious Adverse Events Form must also be completed according to the SAE reporting timeline described in Section 8.4.1, ie, within 24 hours of having become aware of the event, even if all details are not available.

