5.6.2. Adverse Events

The verbatim terms used in the CRF by investigators to identify adverse events will be coded using the Medical Dictionary for Regulatory Activities (MedDRA). Any AE occurring at or after the initial administration of study intervention through the day of last dose plus 2 days is considered to be treatment emergent. AEs with onset date > date of last dose of double-blind study intervention plus 2 days will be assigned to follow-up phase. If the event occurs on the day of the initial administration of study intervention taken is not entered as 'Not Applicable' in the database), then the event will be considered as treatment emergent. If the event date is recorded as partial or completely missing, then the event will be considered to be treatment emergent unless it is known to be prior to the first administration of study intervention based on partial onset date or resolution date. All reported adverse events will be included in the analysis. For each adverse event, the number and percentage of participants who experience at least 1 occurrence of the given event will be summarized by planned intervention group.

Summary tables will be provided for treatment-emergent adverse events:

- AEs (all AEs, and AEs with incidence of at least 5% in any treatment group)
- Serious AEs (SAEs)
- AEs leading to discontinuation of study intervention
- AEs by severity
- AEs by relationship to study intervention
- AEs of special interest (See Appendix 6.6 for list of adverse events in each category)

In addition to the summary tables, listings will be provided for participants who had:

- SAEs
- AEs leading to discontinuation of study intervention
- AEs of special interest

A listing of participants who died will be provided.

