6.6. Appendix 6 Adverse Events of Special Interest

AE Special Interest	Event Type
Category	
Somnolence	Somnolence
Cataplexy	Cataplexy
Sleep paralysis	Sleep paralysis
Complex, sleep-related	Confusional arousal
behaviors/parasomnias	Somnambulism
	Sleep terror
	Bruxism
	Sleep sex
	Sleep-related eating
	disorder
	Sleep behaviour disorder
	Catathrenia
Fall	Fall
Motor vehicle accident	Motor vehicle accident

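### The SAP builds the AESI table from a finite list and does not use the AESI eCRF pages, so an event that is an AESI only under the protocol's open wording can be left out

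*Protocol*

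**What the plan says.** Protocol 8.4.6 sets out six AESI categories, and its wording is open in places. Somnolence comes with illustrative examples: "Somnolence (eg, sleepiness, drowsiness". Parasomnias are introduced as examples and not as a complete set: "Complex, sleep-related behaviors/parasomnias such as confusional arousals", followed by six more. Motor vehicle accident has three alternative names: "Motor vehicle accident (also referred to as a road traffic accident, traffic collision, or a car accident". Cataplexy, sleep paralysis and fall are explained by short descriptions.

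The protocol also creates a separate record of these events. Section 8.4.2 makes AESIs the exception to open-ended questioning, so investigators ask about them directly at each visit. Section 8.4.6 adds: "When reported, the investigator will be required to complete additional eCRF pages for AESI".

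SAP 5.6.2 starts from dictionary coding: "The verbatim terms used in the CRF by investigators to identify adverse events will be coded using the Medical Dictionary for Regulatory Activities (MedDRA". Its summary table for these events is specified as "AEs of special interest (See Appendix 6.6 for list of adverse events in each category". Appendix 6.6 has the same six categories, with a column headed Event Type. Five categories have one entry each and parasomnias have eight, one of which, "Sleep behaviour disorder", is not named in the protocol. There is no entry for other or unspecified events. SAP 5.6.2 also plans an AESI listing, without repeating the reference to the appendix. The AESI eCRF pages are not mentioned.

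**The concern.** The protocol and the SAP define an AESI in two different ways. Under the protocol, the investigator decides at the visit, using a definition that admits events beyond those named. Under the SAP, a fixed list decides afterwards. Nothing says which prevails when they disagree, or that anyone looks for disagreements.

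AESIs are part of the protocol's safety endpoint and are to be summarised separately. This is the first study of the drug in this population, and its planned size is small. An AESI table that leaves out events the investigators were told to record as AESIs would not answer the question the protocol set.

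There is a further effect within the report. Under protocol 8.5.1, having an AESI calls for a blood sample for drug, metabolite and alpha-1-acid glycoprotein levels if it can be taken within 15 hours of the last dose, and section 9.4.4 tabulates those results. The site must decide on that sample before any coding is done, so it follows the protocol definition. The pharmacokinetic tabulation and the AESI safety table could then rest on different sets of participants.

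**Working it through.** The plan states no figure to reproduce, and no formula applies. The check sets the two definitions side by side.

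| Category | Protocol 8.4.6 | SAP Appendix 6.6 |
|---|---|---|
| Somnolence | named, with two open-ended examples | one entry |
| Cataplexy | named, with a description | one entry |
| Sleep paralysis | named, with a description | one entry |
| Parasomnias | seven named, as examples | eight entries |
| Fall | named, with a description | one entry |
| Motor vehicle accident | named, with three alternative names | one entry |

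**Term count.** The protocol names 5 + 7 = 12 events. The SAP lists 5 + 8 = 13. All 12 are on the SAP list, so 12 − 12 = 0 are missing and 13 − 12 = 1 is added.

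**What happens to each kind of event.**

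1. *An event named in both documents.* It has an entry in Appendix 6.6, so no conflict arises.
2. *An event reported under a synonym or description, such as drowsiness or a road traffic accident.* The result depends on two things the documents do not give: how MedDRA codes the reported words, and what Event Type means. Event Type could be a MedDRA preferred term, a lower-level term or a field on the AESI eCRF page. The result is undetermined.
3. *A parasomnia outside the eight listed.* The protocol's open wording makes it an AESI, so it gets AESI pages. Appendix 6.6 has no row for it. This follows from the two texts alone and needs no knowledge of the dictionary.

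**Where a missed event still appears.** SAP 5.6.2 includes all reported adverse events in the analysis and summarises each one by intervention group. An event in case 3 is therefore in the all-AE table. That table counts participants by individual event. It does not give participants per AESI category, which is the purpose of the AESI table.

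**Scale of one participant.** With 86 randomised 1:1, each arm has about 86 / 2 = 43. One participant omitted from a category changes that arm's percentage by 1 / 43 = 2.3 percentage points. This shows the weight of one omission. It does not estimate how many there will be, because the documents give no AESI rate and no rate of off-list coding.

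**The case against.** The strongest reply is that coding exists to map reporters' words to standard terms, so sleepiness, falling down or a car accident may well reach a listed event. Event Type is also not declared to be a dictionary level, whereas SAP 6.5 names the base preferred term explicitly when it summarises medications. If Event Type is a field on the AESI page, nothing recorded under a listed type is lost. Silence about the pages is not the same as excluding them. The list contains every event the protocol names and adds one, which widens capture. A missed event stays in the all-AE table, and protocol 9.4.3 allows narratives and listings for AESI participants. AESI summaries are descriptive, with no test or decision rule attached.

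Most of this stands. A reader might infer that the protocol's synonyms are lost, even that the motor vehicle accident category would be empty whatever happened. The documents do not support that, because it turns on MedDRA content they do not contain. A reader might also take the extra SAP entry as evidence of undercounting, but it points the other way.

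Two things survive. A parasomnia outside the eight has no row whichever meaning of Event Type is intended. And the uncertainty over Event Type supports clarifying the SAP: two programmers could produce different AESI tables from the same data.

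**Conclusion.** The point holds as a conflict between two stated definitions with a limited consequence. An event the investigator records as an AESI under the open wording can be left out of the AESI table, and the clear case is a parasomnia outside the eight listed. The documents do not show that such an event will occur or that the table will undercount. They also do not show that AESIs vanish from the safety report, since the all-AE table retains them.

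The size of any undercount cannot be computed. One omitted participant is worth about 2.3 percentage points in an arm of 43, assuming all 86 are randomised and dosed. The conclusion rests on reading Appendix 6.6 as the complete rule for the table, which is how SAP 5.6.2 presents it. It would fall away if a programming specification outside these documents already brought in the AESI pages and provided for unlisted events.

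**What to change.** Make four changes in SAP 5.6.2 and Appendix 6.6:

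- Count an event as an AESI if an AESI eCRF page was completed for it or its coded term is on the list. Apply the same rule to the table and the listing.
- State the MedDRA level at which the listed terms are matched.
- Add a row for other parasomnias, so that events admitted by the protocol's open wording have a place.
- Before database lock, and blinded to treatment, review every event with an AESI page whose coded term is off the list. Document the category assigned. The protocol does not say whether the page records a category; if it does not, assign one at this review.

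The cost is SAP wording, a merge with data the protocol already requires, and a short blinded review. Trial conduct is unaffected. AESI counts may become slightly higher, and a footnote should state the rule so that the table can be compared with other studies in the program.

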8.5. Pharmacokinetics

Plasma samples will be used to evaluate the PK of seltorexant. Plasma collected for PK may additionally be used to evaluate safety or efficacy aspects that address concerns arising during or after the study period. Genetic analyses will not be performed on these plasma samples. Participant confidentiality will be maintained.

8.5.1. Evaluations

Blood samples for the determination of plasma concentrations of seltorexant, its M12 metabolite,

and alpha-1-acid glycoprotein, will be collected from participants per the SoA.

In addition, blood samples will be collected for determination of plasma concentrations of seltorexant, its M12 metabolite, and alpha-1-acid glycoprotein in participants who discontinue study drug for an AE, have an AESI, or have an SAE if the sample can be obtained within 15 hours of the last study drug administration.

Blood samples will be collected to determine alpha-1-acid glycoprotein levels at each PK collection day (as indicated in the SoA) to calculate the unbound concentrations.

During the DB treatment phase, blood samples for PK will be collected from all participants, including placebo-treated participants, but samples from placebo-treated participants will not be analyzed for PK. These samples will be stored and may be analyzed if needed (eg, suspicion of an incorrect treatment assignment).

Additional information about the collection, handling, and shipment of biological samples can be found in the laboratory manual.

The exact date and time of PK blood sample collection must be recorded, along with all concomitant medications (dose, drug, start and stop date). Study drug dosing time on the day before each PK sample collection will be accurately recorded by exact dosing date and time by the participant or his study partner in the participant medication diary. In addition, in participants who have ongoing AE leading to discontinuation every effort will be made to collect additional PK sample.

8.5.2. Analytical Procedures

Pharmacokinetics

Plasma samples will be analyzed to measure concentrations of seltorexant and its M12 metabolite using a validated, specific, and sensitive liquid chromatography/mass spectrometry/mass spectrometry (LC-MS/MS) method by or under the supervision of the sponsor.

Alpha-1-acid glycoprotein (AGP) levels will be determined. AGP will be conducted under Good Clinical Practice (GCP).

8.5.3. Pharmacokinetic Parameters and Evaluations

Plasma concentration-time data will be displayed by visit date and time for seltorexant and its M12 metabolite. The alpha-1-acid glycoprotein levels will be tabulated for each participant.

8.6. Genetic and Pharmacogenomic Evaluations

Blood samples will be collected from participants who consent separately to this optional component of the study (where local regulations permit) to allow for genotyping of the CYP2C9 and CYP3A4 genes, which may influence metabolism of seltorexant. Samples will also be assessed for APOE genotype.

8.7. Biomarkers

Biomarker blood samples will be collected to explore biomarkers related to AD, including but not limited to: p217+tau, A $\beta42/40$ levels and ratio, and neurofilament light chain (NfL).

Biomarker assays may be added or deleted based on scientific information or technical innovations under the condition that the total volume of blood collected will not be increased.

Stopping Analysis

Biomarker analyses are dependent upon the availability of appropriate biomarker assays and clinical response rates. Biomarker analysis may be deferred or not performed, if during or at the end of the study, it becomes clear that the analysis will not have sufficient scientific value for biomarker evaluation, or if there are not enough samples or responders to allow for adequate biomarker evaluation. In the event the study is terminated early or shows poor clinical efficacy, completion of biomarker assessments is based on justification and intended utility of the data.

8.8. Immunogenicity Assessments

Not applicable.

8.9. Health Economics

Health Economics/Medical Resource Utilization and Health Economics parameters are not evaluated in this study.

9. STATISTICAL CONSIDERATIONS

Statistical analysis will be done by the sponsor or under the authority of the sponsor. A general description of the statistical methods to be used to analyze the efficacy and safety data is outlined below. Specific details will be provided in the Statistical Analysis Plan.

9.1. Statistical Hypotheses

This study is designed to show that the treatment effect in improving agitation and aggression (as measured by change from baseline on Day 43 in NIPC A+A score) of seltorexant 20 mg is superior to placebo in participants with probable AD with clinically significant agitation/aggression.

If μ_T is the mean change in NPI-C A+A for seltorexant 20 mg group and μ_P is the mean change in NPC A+A for the placebo group, then the hypothesis can be written as follows:

 $H_0: \mu_T - \mu_P \ge 0 \text{ vs.}$ $H_1: \mu_T - \mu_P < 0$

Superiority in seltorexant 20 mg can be concluded if the one-sided p-value for the testing of the hypothesis above is less than 0.1 (equivalently, the two-sided p-value for the testing of the hypothesis above is less than 0.2, with greater improvement in the 20 mg group).

9.2. Sample Size Determination

Assuming a treatment difference of 5 points in change from baseline in NPI-C A+A score between

seltorexant 20 mg and placebo, a standard deviation of 10 (effect size of 0.5), 15% drop-out rate during the 6-week double-blind phase, 86 participants (randomized in 1:1 ratio to placebo and seltorexant 20 mg) will need to be enrolled in the double-blind phase, in order to achieve 80% power to detect treatment difference, at one-sided 0.1 significance level.

9.3. Populations for Analysis Sets

For purposes of analysis, the following analysis sets are defined:

Analysis Set	Description
Screened	All participants who sign the ICF
Randomized	All participants who were randomized in the study
Full	All randomized participants who take at least 1 dose of study intervention
Safety	All randomized participants who take at least 1 dose of study intervention.

9.4. Statistical Analyses

For all efficacy endpoints, descriptive statistics of the actual values and the change from baseline to each postbaseline time point in the double-blind phase will be presented by intervention group.

The statistical analysis plan will be finalized prior to DBL and it will include a more technical and detailed description of the statistical analyses described in this section. This section is a summary of the planned statistical analyses of the most important endpoints including primary endpoint.

9.4.1. **Primary Endpoint(s)**

The analyses of efficacy endpoints will be based on the full analysis set.

The primary efficacy endpoint is the change in NPI-C A+A score from baseline to Day 43.

There are two estimands defined for the primary efficacy endpoint. The primary estimand is Estimand 1, and the supplementary estimand is Estimand 2.

Estimand 1:

Study Intervention:

- Experimental: seltorexant
- Control: placebo

Population: participants with probable AD with clinically significant agitation/aggression, as reflected by the inclusion/exclusion criteria.

Variable: change in NPI-C A+A from baseline to Day 43.

Summary measure: difference in treatment means between placebo and seltorexant 20 mg.

Intercurrent events and corresponding strategies:

• Treatment discontinuation of study drug (Hypothetical strategy: as if the intercurrent event had not occurred)

- Switch of treatment (Hypothetical strategy: see above)
- Allowed rescue medication (Treatment policy strategy: all observed values of the endpoint are used regardless of whether or not the participant had experienced this intercurrent event)

Estimand 2:

All components are the same as Estimand 1, except for intercurrent events and corresponding strategies.

Intercurrent events and corresponding strategies:

- Treatment discontinuation of study drug (Treatment policy strategy: all observed values of the endpoint are used regardless of whether or not the participant had experienced this intercurrent event)
- Switch of treatment (Hypothetical strategy: as if the intercurrent event had not occurred)
- Allowed rescue medication (Treatment policy strategy: all observed values of the endpoint are used regardless of whether or not the participant had experienced this intercurrent event)

Main Analysis Under Estimand 1

The comparison between seltorexant 20 mg and placebo will be performed using the appropriate contrasts in a MMRM with main comparison at Day 43. The MMRM will include stratification factors (see Section 6.3), time, intervention group (placebo and seltorexant 20 mg) and time-by-intervention interaction as factors, and baseline NPI-C A+A as a covariate. Difference in least square means and 2-sided 80% CI will be presented.

Main Analysis Under Estimand 2

The copy reference (CR) multiple imputation (MI) method will be performed. A mixed model (which will include the same factors and covariates as in the main analysis for Estimand 1) will be applied to each imputed dataset (with the CR MI method), and the Rubin's rule will be used to combine results from each imputed dataset.

9.4.2. Secondary and Tertiary/Exploratory Endpoint(s)

The analyses for other efficacy endpoints and the analyses for exploratory endpoints (including cognitive symptoms, actigraphy and data obtained from the off-body touchless sensors, if applicable) that are not described in the protocol will be described separately in the SAP. There is no multiplicity adjustment for other efficacy endpoints.

